# 2. To preliminarily explore the impact of the MiNDToolkit intervention on relevant carer variables, such as wellbeing, distress, quality of life.

Data analyses: the data analyses will be used to assess: (i) the degree of completion of each outcome measure and (ii) potential impact of the intervention on each.

(i) We will provide an estimate of the number of individuals completing each outcome measure and provide a 95% confidence interval with each estimate. We will also assess the number of missing items and for each with attention to any particular pattern. The distribution of each measure will be inspected to assess the possibility of 'ceiling' or 'flooring' effects. which would make an outcome inappropriate for a trial.

(ii) A comparison will be made between the MiNDToolkit and treatment as usual group with respect to each of the above outcome measures. Assuming a Normal distribution (or after an appropriate transformation) the difference in means will be estimated with a 95% confidence interval. The difference will also be expressed as a 'generic' (or Cohen's) Effect Size in order to assess the relative impact on each measure. The within group standard deviation will also be estimated, with 95% confidence intervals, which will be useful for future studies.

## 3. ETHICAL CONSIDERATIONS

#### 3.1 Research Ethics

The research clinic will be run in compliance with the principles of the Declaration of Helsinki (1996) and Good Clinical Practice (GCP-ICH 1997). All researchers working in the clinic will receive training in GCP-ICH guidelines and any relevant future acts and regulations.

Participant information sheets, consent forms, and the study protocol (created with reference to the National Research Ethics Service guidance and input from Patient and Public Involvement) will make it clear that participation is voluntary and participants can withdraw at any time without giving a reason and without the care they receive from the NHS being affected.

Some of the measures used are either routine in the NHS clinics or have been validated for the neurodegenerative conditions involved in this project. Withdrawal may occur for several reasons, including change in circumstances (e.g. health status of person with MND), intolerance of the assessments/intervention by the carer, or a change of carer. If a participant moves out of the area, participation can still continue with their consent. If the person with MND passes away, the carer will be automatically withdrawn from the study and a condolence letter will be sent via post or email from the central team informing them that their account will be inactivated so that they no longer receive notifications sent from the platform. Participant assessments will be tracked by the MiNDToolkit platform to prevent unnecessary repetition of tests or questionnaires. Furthermore, following input from the trial management group and PPI, participants and HCPs will be allowed continued access to the MiNDToolkit following the end of the trial while funds are available for running costs enabling the platform to be open.

#### 3.2 Safety

The risk of a serious adverse event arising from any of the research activities involved in this study is extremely low. Patients with MND about whom data is being anonymously collected are under the care of specialist clinics for their condition during the period of the study. The main focus of the study is on the health and wellbeing of the carer, and the intervention aims to provide psychoeducation and patient management suggestions to the carer rather than offering a clinical intervention to the person with MND.

The Trial Management Group (TMG) will assist with developing the design, co-ordination and strategic management of the trial. They will oversee any safety issues that arise during the trial. The membership, frequency of meetings, activity (including trial conduct and data review) and authority will be covered in the TMG terms of reference.

Carers will be given the opportunity to report any adverse events that they feel are related to the intervention at the post-intervention assessment, and this will be monitored by

the CI and site PI. If a researcher becomes concerned about the safety or welfare of a carer or the person they care for during the study period, they will encourage the carer to contact their GP, and sign-post them to local sources of support. If a carer indicates on the online platform that they are experiencing thoughts of self-harm (Patient Health Questionnaire 9 – item 9), the CTU and linked HCPs will be automatically notified and a list of contact details for support and crisis lines will appear for the carer at the end of the testing battery.

| Name                    | Affiliation                 | Role and responsibilities              |
|-------------------------|-----------------------------|--|
| [name] | School of Health Sciences,  | Chief Investigator                     |
|                         | University of East Anglia   |  |
| Professor               | Norwich Medical School,     | Professor of Dementia Research         |
| [name]      | University of East Anglia   |  |
|                         |                             |  |
| [name]            | Norfolk and Norwich         | Principal Investigator - MND Care and  |
|                         | University Hospital         | Research Network Coordinator,          |
|                         |                             | Norfolk                                |

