#### c) Screening/Baseline measures (0 months)

If consent is provided, participants will then be asked to complete the screening and baseline assessment questionnaires online. Of note, some measures (e.g. ALSFRS-R adapted) were modified in terms of sentence construction, as they are being completed by the carer. For example, instead of 'normal speech processes', it now reads 'They have normal speech processes. Sentences became longer to ensure they were clearer for the carer, following feedback from PPI test users and clinicians. Additionally, some questions were further explained to help carer in completing the information. For example, please enter month and year. We also had to break down questions set up as tables on paper, as they are now presented as separate questions due to the online nature of the questionnaire where only one question is presented at a time. This was a point raised by PPI members, who asked for a simple view of the questionnaires, e.g. not presented as pages (as in paper questionnaires), but as one question at a time.

This assessment will include the following (in **bold** are domains assessed by each instrument):

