#### Baseline measures

Outcome measures being tested:

- The Patient Health Questionnaire 9 (PHQ-9; Kroenke et al., 2003) is a very brief multipurpose self-rated instrument for screening, diagnosing, monitoring and measuring the severity of depression for the carer.
- The Generalized Anxiety Disorder Questionnaire 7 (GAD-7; Kroenke et al., 2007) is a very brief self-rated questionnaire measuring for symptoms of generalized anxiety disorder for the carer.
- The Adapted Client Service Receipt Inventory (CSRI; Beecham & Knapp, 2001) is a tool to collect information on the range of services and supports currently being utilised by the person with MND.
- The Carer Experience Scale (CES; Al-Janabi et al., 2008) is a short, self-report measure for the carer of their caring experience for use in economic evaluation that assesses care-related quality of life in multiple domains including activities outside caring, fulfilment from caring, and relationship with the care recipient.
- ICEpop CAPability measure for Adults (ICECAP-A; AI-Janabi et al., 2012) is the short measure of wellbeing for the carer. The ICECAP-A is a measure of capability of the general adult (18+) population for use in economic evaluation.
- Acceptance and Action Questionnaire II (AAQ-II; Bond et al., 2011) is a 7-item selfreport questionnaire assessing people's general levels of **psychological flexibility**, the ability to be open, present-focused, and to change or persist in behaviour according to changing internal and external circumstances.

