#### Measures that trigger modules in intervention:

- Adapted Frontotemporal Dementia Rating Scale (FRS; [name] et al., 2010) is a 30item, carer interview-based measure of disease severity in FTD and has been validated in MND.
- MiND-B (from screening)

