6.4 Missing Data and Invalid data

Trial questionnaires are completed online and a participant cannot ‘advance’ from one item until it is completed. However, it is possible for a participant to abandon entry online and not complete all questionnaires. The proportion doing this will be calculated together with a 95% confidence interval. Also, not all online entry was completed within the intended 30 days of six month follow-up. The number falling outside of 30 days will be calculated, again with a 95% confidence interval.

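### A carer who endorses PHQ-9 item 9 is shown the crisis-line list only at the end of a battery that can be abandoned but not skipped through; showing it at the answer as well is a cheap improvement

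*Protocol*

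**What the plan says.** Protocol 3.2 gives two responses to a carer who indicates thoughts of self-harm on PHQ-9 item 9. For staff, "the CTU and linked HCPs will be automatically notified". For the carer, "a list of contact details for support and crisis lines will appear for the carer at the end of the testing battery". No earlier display to the carer is described.

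The same section has two broader provisions. The first begins "If a researcher becomes concerned about the safety or welfare of a carer or the person they care for during the study period", and has the researcher point the carer to the GP and to local support. The second concerns the Trial Management Group: "They will oversee any safety issues that arise during the trial".

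Two passages describe how the battery runs. Protocol 2.5 c describes an online questionnaire "where only one question is presented at a time". SAP 6.4 says a participant cannot move on "from one item until it is completed. However, it is possible for a participant to abandon entry online and not complete all questionnaires". It plans to estimate the proportion who abandon, with a 95% confidence interval.

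Appendix 1 of the Protocol gives about 30 minutes for the baseline session and for each post-intervention session. It schedules the PHQ-9 at baseline, post-intervention and second post-intervention. Neither document states the order in which the instruments appear on screen, or whether a part-finished battery can be resumed.

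**The concern.** Of the two item-9 responses, the list is the one that reaches the carer directly, without a member of staff having to act. As written, it depends on the carer finishing whatever questionnaires remain. The carer cannot jump ahead to it, and the SAP itself expects some carers to stop part-way.

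What is at stake is the carer's welfare. The point does not touch the sample size, the error rates or any planned estimate. It deserves a line because the Protocol makes carer health and wellbeing the main focus of the study, and because the remedy is small.

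**Working it through.** The plan gives no figure to reproduce, and no rate from which to calculate one. The check sets the provisions side by side and then bounds what can lie between item 9 and the list.

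**Step 1: does the gap follow from the text?**

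- The list appears at the end of the battery (Protocol 3.2).
- Questions come one at a time (Protocol 2.5 c), and each must be completed before the next (SAP 6.4). The carer therefore cannot skip to the end.
- Entry can be abandoned (SAP 6.4). A carer who endorses item 9 and then stops does not reach the end in that session.

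The gap follows, provided at least one instrument comes after the PHQ-9.

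**Step 2: how many instruments could come after the PHQ-9?**

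Taking each listing as the screen order is an assumption.

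| Assumed order | Instruments after PHQ-9 | Count |
|---|---|---|
| PHQ-9 shown last | none | 0 |
| Appendix 1, carer (self) rows, post-intervention column | GAD-7, CES, ICECAP-A, AAQ-II | 4 |
| Protocol 2.5, post-intervention assessment, carer list | GAD-7, CES, ICECAP-A, CSRI, AAQ-II | 5 |
| Protocol 2.5 c, baseline listings in sequence | GAD-7, CSRI, CES, ICECAP-A, AAQ-II, FRS, person-with-MND proforma | 7 |

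The baseline count leaves out the MiND-B, which is carried over from screening. The post-intervention text names the CSRI both among the measures about the person with MND and among the carer measures. If it is given only once, in the earlier place, the count of 5 becomes 4. The range under the listings is 4 to 7 either way.

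**Step 3: how long?**

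The session lasts about 30 minutes in total and includes the PHQ-9 itself. In the Appendix 1 and post-intervention orders, the measures about the person with MND also come before it. The time from item 9 to the list is therefore only part of 30 minutes, and close to zero if the PHQ-9 is last.

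**Step 4: how often does it arise?**

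The PHQ-9 is scheduled at three time points. The second post-intervention assessment applies only to controls who cross over and to intervention carers who choose to continue (Protocol 2.5, Stage 3; Appendix 1). Up to 30 carers are planned. Without endorsement or abandonment rates, no headcount can be derived.

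**The case against.** The strongest reply is that the main safeguard is already in place. On a plain reading, the notice to the trials unit and linked professionals is triggered by the carer's answer; the phrase about the end of the battery qualifies only the list. Researchers act on welfare concerns, and the Trial Management Group oversees safety. The gap also needs two things to happen together: the PHQ-9 must come before the end, and a carer must stop after endorsing item 9. Finally, a message in mid-battery could disturb completion and later answers, in a study whose purpose includes testing those measures. End placement with a staff alert is a defensible design.

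Most of this stands, and it limits the point to an improvement. It does not remove it: nothing in either document makes the list available to a carer who stops, and showing it twice takes nothing away from the alert.

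A reader might infer more in three ways, none of which the documents support.

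- **That a carer who abandons gets no response at all.** The automatic notice is not tied to completion or submission. At post-intervention, a reminder after one week and a telephone call a week later also follow non-completion. Those steps serve data collection, and none is described for an unfinished baseline battery, but the call is human contact.
- **That a large number of items can be counted between item 9 and the list.** The Protocol says the AAQ-II "is a 7-item selfreport questionnaire assessing" psychological flexibility and the FRS "is a 30item, carer interview-based measure of" disease severity. But the FRS is used here in adapted form, and SAP 5.5 describes the MiND-B with additional FRS adapted questions, so the number of FRS questions shown is not known. Two of the three listings also place the FRS before the PHQ-9. An item count is not safe.
- **That the delay is a full 30 minutes at every PHQ-9 time point for every carer.** Steps 3 and 4 of the working show why not.

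**Conclusion.** The point holds as a modest patient-safety improvement. Under Protocol 3.2 as written, a carer who endorses item 9 and then abandons entry would not see the support and crisis-line list in that session.

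The size runs from close to nil, if the PHQ-9 is shown last, to 4 to 7 intervening instruments and part of a session of about 30 minutes, if the screens follow one of the documents' listings. This rests on two assumptions: that the Protocol describes every display of the list, and that a listing may reflect screen order. The participant information sheet is not among the documents, so whether carers already hold the same contacts cannot be judged.

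Nothing here says that the alert would fail. Nor does the point extend to the way adverse events are collected from carers who leave early. A reader might infer that, but the withdrawal form is not among the documents and may already ask.

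**What to change.** Amend Protocol 3.2 so that the support and crisis-line list is displayed as soon as a carer endorses item 9, and again at the end of the testing battery. The rest of the section can stay as it is.

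The cost is one changed sentence and what should be a small platform edit, since the platform already reacts to item 9 and shows one question per screen. The documents give no cost figure, so calling it cheap is a judgement. The downsides are a brief interruption in the battery and a possible slight effect on the answers that follow.

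Parts of SAP 6.3 and 6.4 are in the past tense, which suggests that follow-up may already have been under way when the SAP was written. If so, the benefit falls on any assessments still to come and on a larger trial that uses the same platform.

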#### 3.3 Trial Management Group (TMG)

## 4. DATA MANAGEMENT, CONFIDENTIALITY AND DATA STORAGE

Essential trial issues, events and outputs, including defined key data points, will be detailed in the MiNDToolkit trial Data Management Plan.

We follow standard good research practices within our departments, to ensure confidentiality of electronic and hard copy data, in keeping with most recent data protection regulations. All data will be handled in accordance with the Data Protection Act (2018) and the EU GDPR. Participants will be assured that confidentiality will be maintained unless there is evidence of risk of harm to self or others.

Any paper copies of personal trial data will be kept at the participating site in a secure location with restricted access. Following consent, identifiable participant data will be kept on the trial database to allow authorised members of the trial team to contact participants in order to arrange appointments and assessments. Only authorised trial team members will have password access to this part of the database. At trial enrolment the patient will be issued a participant identification number and this will be the primary identifier for the participant and their study data.

The participant's consent form will contain their name. These will be primarily stored in the online database, but will also be kept and will be archived at the trial site, and copies may also be accessed and stored at NCTU for monitoring purposes. Consent forms will not be kept with any additional participant data.

Data will be entered under the participants' platform PID number onto the central database stored on the servers based in Amazon Web Services' London EU Region. This will also include personally identifiable data including names, email addresses and contact phone numbers. Access to the database will be via unique, individually assigned (i.e. not generic) usernames and passwords, and only accessible to members of the MiNDToolkit trial team at UEA, and external regulators if requested. Each participant's data will also be accessible to the specific site team responsible for their recruitment and delivery of the intervention. The servers are protected by firewalls and are patched and maintained according to best practice. The physical location of the servers is protected physically and environmentally in accordance with University of East Anglia's General Information Security Policy 3 (GISP3: Physical and environmental security).

The database and associated code have been developed by AAH Software Limited, in conjunction with the MiNDToolkit trial team. The database software provides a number of features to help maintain data quality, including; maintaining an audit trail, allowing custom validations on all data, allowing users to raise data query requests, and search facilities to identify validation failure/ missing data.

After completion of the trial the database will be retained on the servers of AAH Software Limited and the dataset for analysis will be transferred to servers at UEA for on-going analysis of secondary outcomes.

The identification, screening and enrolment logs will be held locally by the trial site. This will either be held in written form in a locked filing cabinet or electronically in password protected form on hospital computers. De-identified participant data including screening logs and

withdrawal forms may be shared between sites and the central NCTU team via a secure Microsoft OneDrive folder hosted by NCTU. After completion of the trial the identification, screening and enrolment logs will be stored securely by the sites for 5 years unless otherwise advised by NCTU.

In accordance with good practices locally we will hold non-identifiable data for a minimum of 10 years within the Faculty of Medicine and Health Sciences, UEA. Individual data will be anonymised and indexed by an alphanumeric reference code, which is kept separately from other data and retained only by the study team. It will not be possible to identify participants' individual data without this code. All non-identifiable data will be kept within a locked building with keycard access doors. Anonymised electronic data will be stored and managed using databases encrypted with industry standard cryptographic methods and protected by passwords. Hard copy data will be stored in a locked cabinet in a locked room to which only the study team have access.

Relevant information will be shared between other members of the department (of the participants who will be seen in departmental clinics), and UEA collaborators, and with researchers undertaking other ethically approved research including national and international collaborations, who all adhere most recent data protection regulations and confidentiality. This information will be anonymized prior to sharing. If participant identifiable data is required (for example to contact participants regarding upcoming research projects), their identifiable information will not be linked to the current research project but rather stored on the clinic databases for which consent has previously been sought.

### 5. COMPLAINTS

A system is in place that enables complaints to be directed either the Head of School, where the Chief Investigator is based, or the respective NHS Trust independent patient liaison service (PALS). Contact details for all of these sources are provided on the participant information sheet.

## 6. SPONSORSHIP AND INDEMNITY

This study will be sponsored by UEA. UEA has appropriate insurance policies in place to provide professional indemnity and public liability cover. Medical personnel on the study are also advised to have additional personal medical indemnity.

## Appendix 1. Schedule of Assessment: MiNDToolkit Feasibility Study

|   | Consent +
Screening
measures | Baseline
measures | MiNDToolkit
Intervention
(0 – 3 months) | Post-
intervention
Assessment
(within 1 month | Second post-
intervention
assessment
(0-6 months)                                     |
|---|------------------------------------|----------------------|---|--|--|
|   | (0 months)                         | (0 months)           |   | after end of
intervention)                          | group
participants who
continue to use
modules or cross
over from control
group |
| Online session
length (minutes
approx.) | 15                                 | 30                   | 10 to 20                                      | 30   | 30   |
| Carers (about
MND patients)                |                                    |                      |   |  |  |
| MiND-B  | Ø                                  |                      |   | Ø  |  |
| ALSFRS-R                                      | Ø                                  |                      |   | Ø  | Ø  |
| FRS adapted                                   |                                    | M                    |   | R  | M  |
| CSRI adapted                                  |                                    | M                    |   | Ø  | M  |
| Socio-
demographic,
medical history     |                                    | Ŋ                    |   |  |  |
| Carers (self)                                 |                                    |                      |   |  |  |
| Informed Consent                              | Ŋ                                  |                      |   |  |  |
| Socio-
demographic,
medical history     | Ŋ                                  |                      |   | Ø  | ☑  |
| PHQ-9   |                                    | Ŋ                    |   | Q  | R  |
| GAD-7   |                                    | M                    |   | R  | M  |
| CES   |                                    | M                    |   | R  | M  |
| ICECAP-A                                      |                                    | Ŋ                    |   | Q  | Ø  |
| AAQ-II  |                                    |                      |   | Ø  | ☑  |
| Semi-structured
Interview                  |                                    |                      |   |  |  |
| MiNDToolkit
Intervention                   |                                    |                      | 2 2 2   |  |  |
| НСР   |                                    |                      |   |  |  |
| Fidelity Monitoring                           |                                    |                      | M   | Ø  | R  |
| Semi-structured
Interview                  |                                    |                      |   |  |  |

PHQ = Patient Health Questionnaire, GAD = Generalize Anxiety Disorders scale; MiND-B = MND Behavioural Instrument; ALSFRS-R = ALS Functional Rating Scale-Revised; CES = Carer Experience Scale; ICACAP-A = ICEpop CAPability measure for Adults; AAQ-II = Acceptance and Action Questionnaire II; CSRI = The Client Service Receipt Inventory; FRS = Frontotemporal Dementia Rating Scale
